3 LIST OF ABBREVIATIONS

ACS	:	Acute Coronary Syndrome
ADP	:	Adenosine Diphosphate
AE	•	Adverse Event
ALT	•	Alanine Aminotransferase
ALP	•	Alkaline Phosphatase
ANOVA	•	Analyses of variance
AST	•	Aspartate Aminotransferase
AUC	•	Area Under the Curve
BLQ	•	Below Limit of Quantification
BMI	•	Body Mass Index
BUN	•	Blood Urea Nitrogen
CDSCO	•	Central Drugs Standard Control Organization
C _{max}	•	Maximum blood concentration
CLA	•	Central Licencing Authority
CNS	•	Central Nervous System
COA	•	Certificate of Analysis
CRF	•	Case Record/Report Form
CRO	•	Contract Research Organization
CYP	•	Cytochrome P450 enzymes
DCGI	•	Drug Controller General of India
EC	•	Ethics Committee
EC	•	Electrocardiogram
FDA	•	Food and Drug Administration
GCP	•	Good Clinical Practice
GI	•	Gastrointestinal
GLP	•	Good Laboratory Practice
HBV	•	Hepatitis B Virus
hCG	•	Human Chorionic Gonadotropin
HCV	:	Hepatitis C Virus
HCT	:	Hematocrit
HDPE	:	
	:	High Density Polyethylene
HIV	:	Human Immunodeficiency Virus
ICF	:	Informed Consent Form
ICH	:	International Conference on Harmonization
ICMR	:	Indian Council of Medical Research
IPA ID	:	Inhibition Of Platelet Aggregation
IP K EDTA	:	Investigational Product
K ₂ EDTA	:	Di-Potassium Ethylene diamine tetra acetic acid
kg	:	Kilograms
LC-	1:1	Liquid Chromatography-Mass Spectrometry

CONFIDENTIAL

Page 12 of 74

Ipca Laboratories Ltd Version 1.0 (Amendment 3.0)

MS/MS		
LLQ	:	Lower Limit of Quantification
LOQ	:	Limit of Quantification
LSMs	:	Least-Squares Means
MAD	:	Multiple Ascending Dose
MI	:	Myocardial Infarction
mg	:	Milligram
NDA	:	New Drug Application
NRV	:	Non-reportable Value
OTC	:	Over the Counter
OVIS	:	Online Volunteer Information System
PA	:	Posteroanterior
PD	:	Pharmacodynamics
РК	:	Pharmacokinetics
PI	:	Principal Investigator
PPI	:	Proton Pump Inhibitors
РТ	:	Prothrombin Time
PTT	:	Partial Thromboplastin Time
RBCs	:	Red Blood Cells
RBS	:	Random Blood Sugar
RPR	:	Rapid Plasma Reagin
SAD	:	Single Ascending Dose
SAE	:	Serious Adverse Event
SAS	:	Statistical Analysis Software
SD	:	Standard Deviation
SOP	:	Standard Operating Procedure
t _{1/2}	:	The elimination or terminal half-life
T _{max}	:	Time of the maximum measured blood concentration
TTP	:	Thrombocytopenic Purpura
ULN	:	Upper Limit of Normal
UMC	:	Uppsala Monitoring Centre
VASP	:	Vasodilator-Stimulated Phosphoprotein Phosphorylation
WBCs	:	While Blood Cells
WHO	:	World Health Organization
WMA	:	World Medical Association

Ipca Laboratories Ltd Version 1.0 (Amendment 3.0)

Study Design	will receive a sing of either AT-10 of	open label, two-period, crossove gle loading dose followed by 5 d or Clopidogrel in Period 1 and -10 or Clopidogrel) in Period 2.	aily doses (maintenance dos	
	40 subjects are planned to be randomized into the study. Out of this, 20 subjects would be extensive CYP2C19 metabolizers and 20 would be poor CYP2C19 metabolizers. The 20 extensive metabolizers will be randomized on a 1:1 basis into Groups 1 and 3. The 20 poor metabolizers will be randomized on a 1:1 basis into Groups 2 and 4. Subjects who withdraw or are removed from the study will not be replaced.			
	The dosing schem	e is as follows:		
	Group & Sequence	Period 1	Period 2	
	Group 1 (n=10, extensive metabolizers)	AT -10 40mg on Day 1 AT -10 10 mg on Days, 2, 3, 4, 5 & 6	Clopidogrel 300 mg on Day 1 Clopidogrel 75 mg on Days 2, 3, 4, 5 & 6	
	Sequence 1		Days 2, 5, 4, 5 & 0	
	Group 2	AT -10 40 mg on Day 1	Clopidogrel 300 mg on	
	(n=10, poor metabolizers)	AT -10 10 mg on Days, 2, 3, 4, 5 & 6	Day 1 Clopidogrel 75 mg on	
	Sequence 1		Days 2, 3, 4, 5 & 6	
	Group 3	Clopidogrel 300 mg on Day	AT -10 40 mg on Day 1	
	(n=10, extensive metabolizers) Sequence 2	1 Clopidogrel 75 mg on Days 2, 3, 4, 5 & 6	AT -10 10 mg on Days 2, 3, 4, 5 & 6	
	Group 4	Clopidogrel 300 mg on Day	AT -10 40 mg on Day 1	
	(n=10, poor metabolizers)	1 Clopidogrel 75 mg on Days 2, 3, 4, 5 & 6	AT -10 10 mg on Days 2, 3, 4, 5 & 6	
	Sequence 2	_,_, ,		
Food and Fluid Restrictions	each period after prior to dosing un	at 10 hours prior to dosing until each dosing. Water will be res til at least 01 hours post-dose in dosing) after each dosing.	stricted from at least 01 ho	

3CC GLOBAL RESEARCH	Ipca Laboratories Ltd	
rotocol: CBCC/2019/003	Version 1.0 (Amendment 3.0)	Dated: 22/Apr/2021
Housing	All subjects will be housed in the clinic facility from dosing until at least 24 hours post dose after adminis dose in each study period.	
i osture restrictions	Subjects will remain seated upright for the initial 04 necessary movement will be allowed during this allowed to lie down except as directed by the physic adverse events during this restriction period. Thereaft to ambulate freely during the remainder of the study.	period. They will not b ian and secondarily due to
samples for PK analysis	Blood samples (5 mL each) for PK analysis will be c 0.25, 0.5, 0.75, 1, 1.5, 2, 3, 4, 6, 8, 12 and 24 h administration on Days 1 and 6 in each period. On period only the pre-dose sample will be collected.	(Day 2) after study dru
	The pre-dose (0.0 hour) blood sample shall be taken dosing on each dosing day in each period. All post-d will be collected within + 2 minutes (except 24 hou Day 1) of the scheduled time of blood sample collecti	ose samples in each perio ar post dose time point fo
	Note: In each period, 24 hour post dose sample of D pre-dose sample of respective day.	Day 1 will be considered a
samples for PD assessment	Blood samples (2.7 mL each) for PD assessme aggregation, 20μ M ADP) will be taken pre-dose an dose on each dosing day. Additionally, 24 hrs post of day of each period will be collected for assessing PD assessment will be collected using sodium citrate vac samples for aggregometry will be analyzed at the site.	d 0.5, 2 and 6 hours pos dose sample on last dosin . All blood samples for Pl cutainers. (Note: The bloo
	The pre-dose (0.0 hour) blood sample shall be taken dosing on each dosing day in each period. All post-d will be collected within + 2 minutes of the schedu collection.	ose samples in each perio
methodology	Plasma samples will be assayed by a validated LCMS Cliantha Research, Ahmedabad, which is specific Clopidogrel, AT -10 (2-oxo-clopidogrel) and its meta	for the determination of
	Pharmacodynamics:	
statistical comparisons	Pharmacodynamic assessment will be performed us aggregation in whole blood treated with sodium ci ADP induced platelet aggregation will be assessed for each treatment group at each time point assessed on e 6 hours post dose) and 24 hrs post dosing of last dosi change over time for each parameter will also be Groups 1 and 3 will be combined in the analysis ar combined in the analysis.	trate as an anti-coagulan or change from baseline i ach dosing day (0.5, 2, an ing day in each period. The assessed. The data from

CONFIDENTIAL

Page 16 of 74

CBCC GLOBAL RESEARCH	Ipca Laboratories Ltd
Study Protocol: CBCC/2019/003	Version 1.0 (Amendment 3.0) Dated: 22/Apr/2021
	1. Liver function tests (ALT, AST, total bilirubin, and alkaline phosphatase) measured as part of clinical chemistry
	2. Abbreviated physical examination focused on signs of bleeding including but not limited to echymosis, petechiae, and bleeding gums
	Statistical comparison will be made between the change from baseline at each time point between the Groups 1 and 3 (extensive metabolizers) versus Groups 2 and 4 (poor metabolizers) for each treatment (AT -10 and Clopidogrel).
	The incidence of signs of bleeding from the abbreviated physical examination and the incidence of abnormal liver function tests (ALT, AST, total bilirubin, and alkaline phosphatase) will be tabulated for the treatment groups. The incidence of these events will not be formally tested and the comparison will be observational only. The observational comparisons will be made between the AT -10 and Clopidogrel in the extensive metabolizers and poor metabolizers.
	Pharmacokinetics:
	Pharmacokinetic parameters (AUCt, AUCinf, Cmax, tmax, t¼, kel, Cl/F, Vd/F) will be estimated following noncompartmental analysis of plasma concentration time-course data for Clopidogrel, AT -10 (2-oxo-clopidogrel), and MP-H4. PK parameters at steady-state will be estimated for Clopidogrel, AT-10 (2-oxo- clopidogrel), and MP-H4. Statistical comparison of the single-dose and multiple-dose PK parameters of peak (Cmax) and total (AUCt, AUCinf) exposure for the AT-10 and MP-H4 will be made between the AT-10 and Clopidogrel dose groups; between and within metabolizer groups.
	Although this is not a bioequivalence study following PK comparison will be made:
	• PK comparisons will be made for AT -10 and MP-H4 from AT -10 treatment in extensive metabolizers versus Clopidogrel treatment in extensive metabolizers
	• PK comparisons will be made for AT -10 and MP-H4 from AT -10 treatment in poor metabolizers versus Clopidogrel treatment in poor metabolizers
	• PK comparisons will be made for AT -10 and MP-H4 from AT -10 treatments in extensive metabolizers versus AT -10 treatments in poor metabolizers.
	Other PK comparison will be made if deemed appropriate
Safety Assessment	Tolerability and safety will also be assessed.
	Safety assessments will include screening, pre-dose and post-dose vital signs, ECGs, clinical laboratory testing (hematology, blood chemistry, and urinalysis), documentation of AEs and clinical examinations. Coagulation parameters (PT and PTT) will also be assessed at screening, at housing during each period, at 8 hrs post-dose on each dosing day and at exit or early termination.

Page 17 of 74

Ipca Laboratories Ltd Version 1.0 (Amendment 3.0)

[figure not shown]

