Dose-dependent inhibition of platelet aggregation can be seen 2 hours after single oral doses of Plavix. Repeated doses of 75 mg Plavix per day inhibit ADP-induced platelet aggregation on the first day, and inhibition reaches steady state between Day 3 and Day 7. At steady state, the average inhibition level observed with a dose of 75 mg Plavix per day was between 40% and 60%. Platelet aggregation and bleeding time gradually return to baseline values after treatment is discontinued, generally in about 5 days.

Geriatric Patients

Elderly (≥75 years) and young healthy subjects had similar effects on platelet aggregation.

CONFIDENTIAL

Page 23 of 74

Ipca Laboratories Ltd Version 1.0 (Amendment 3.0)

Renally Impaired Patients

After repeated doses of 75 mg Plavix per day, patients with severe renal impairment (creatinine clearance from 5 to 15 mL/min) and moderate renal impairment (creatinine clearance from 30 to 60 mL/min) showed low (25%) inhibition of ADP-induced platelet aggregation.

Hepatically Impaired Patients

After repeated doses of 75 mg Plavix per day for 10 days in patients with severe hepatic impairment, inhibition of ADP-induced platelet aggregation was similar to that observed in healthy subjects. **Gender**

In a small study comparing men and women, less inhibition of ADP-induced platelet aggregation was observed in women.

Pharmacokinetics:

Clopidogrel is a prodrug and is metabolized to a pharmacologically active metabolite and inactive metabolites.

Absorption

[figure not shown]
After single and repeated oral doses of 75 mg per day, clopidogrel is rapidly absorbed. Absorption is at least 50%, based on urinary excretion of clopidogrel metabolites.

Effect of food

Plavix can be administered with or without food. In a study in healthy male subjects when Plavix 75 mg per day was given with a standard breakfast, mean inhibition of ADP-induced platelet aggregation was reduced by less than 9%. The active metabolite AUC0-24 was unchanged in the presence of food, while there was a 57% decrease in active metabolite Cmax. Similar results were observed when a Plavix 300 mg loading dose was administered with a high-fat breakfast.

Metabolism

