6.2 RATIONALE

Requirement of conducting this study:

The growing body of literature implicating CYP2C19 loss-of-function alleles in adverse clopidogrel responses prompted the USFDA to ask the application holder to implement a boxed warning on the clopidogrel package insert stating, "Effectiveness of Clopidogrel bisulfate depends on conversion to an active metabolite by the cytochrome P450 (CYP) system, principally CYP2C19. Consider use of another platelet P2Y₁₂ inhibitor in patients identified as CYP2C19 poor metabolizers". Hence there is a well-established relationship exist between CYP2C19 deficient pharmacogenomic populations and drug response, that results in diminished effectiveness in poor metabolizers.

To overcome the limitations of clopidogrel associated with CYP2C19 metabolism, Ipca has developed AT-10, a prodrug that is metabolically converted, in one CYP-dependent step, to produce the active metabolite of the approved listed drug Plavix (clopidogrel bisulfate tablet, 300 mg; NDA 20839). A major advantage of the pro-drug AT-10 is its more efficient metabolism through one CYP-dependent step, as compared to the two-step process for clopidogrel involving several CYP450 isoenzymes. It is possible that AT-10 may provide a faster and more consistent inhibition of platelet function, thereby producing important clinical benefits for patients. The response to AT-10 may not be influenced by genetic CYP2C19 polymorphisms to the extent of its influence in clopidogrel, thus eliminating the need for characterization of clopidogrel responsiveness and thereby maintaining effectiveness in all patients, including those patients who are identified as CYP2C19 poor metabolizers as well. So in order to explore the PK-PD and safety profile of AT-10 in Indian population the current study has been proposed.

CONFIDENTIAL

Page 32 of 74

Ipca Laboratories Ltd Version 1.0 (Amendment 3.0)

Selection of AT-10 doses for this study:

It is important to note that AT-10 is an intermediate metabolite in the metabolic pathway of Clopidogrel to the active metabolite. Therefore, this study does not represent the first exposure of AT-10 in humans. It does, however, represent the first direct administration of AT-10 to humans. The highest single dose planned for AT-10 is 40 mg and the highest single dose planned for Clopidogrel is 300 mg.

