9.2.2 INVESTIGATIONAL PRODUCT ADMINISTRATION

The randomization will be generated of #40 subjects for each type of metabolizers i.e. extensive and poor, and it will be for each gender group i.e. #20 for each male and female respectively for each type of metabolizers. Total 04 randomization schedule will be prepared. Each randomization schedule should be containing 20 subjects (10 subjects for each sequence). This randomization approach will help in achieving near to equal proportionate distribution of the treatment across the study and between the gender.

CONFIDENTIAL

Page 44 of 74

Ipca Laboratories Ltd Version 1.0 (Amendment 3.0)

As per randomization, IP will be administered as per below scheme on day 1, 2, 3, 4, 5 and 6 in each period. Subjects will be fasting overnight for at least 10.00 hours before IP administration. IP will be administered orally in sitting posture with 240 ± 2 mL of water at room temperature.

Group &	Period 1	Period 2
Sequence		
Group 1	AT -10 40mg on Day 1	Clopidogrel 300 mg on Day 1
(n=10, extensive	AT -10 10 mg on Days, 2, 3, 4, 5 & 6	Clopidogrel 75 mg on Days 2, 3, 4, 5
metabolizers)		& 6
Sequence 1		
Group 2	AT -10 40 mg on Day 1	Clopidogrel 300 mg on Day 1
(n=10, poor	AT -10 10 mg on Days, 2, 3, 4, 5, & 6	Clopidogrel 75 mg on Days 2, 3, 4, 5
metabolizers)		& 6
Sequence 1		
Group 3	Clopidogrel 300 mg on Day 1	AT -10 40 mg on Day 1
(n=10, extensive	Clopidogrel 75 mg on Days 2, 3, 4, 5,	AT -10 10 mg on Days 2, 3, 4, 5 & 6
metabolizers)	& 6	
Sequence 2		
Group 4	Clopidogrel 300 mg on Day 1	AT -10 40 mg on Day 1
(n=10, poor	Clopidogrel 75 mg on Days 2, 3, 4, 5,	AT -10 10 mg on Days 2, 3, 4, 5 & 6
metabolizers)	& 6	
Sequence 2		

Note: In all the periods, IP administration will be done by trained study personnel delegated by the investigator and will be reviewed by quality control / quality assurance personnel. Investigator will be available at site during IP administration. Subjects will be asked to swallow the tablet as a whole without being chewed, crushed or bitten. The time of dosing on Day 01 will be the reference time for all subsequent dosing. Dose 02 to Dose 06 will be administered at an interval of 24 hours of previous dose.

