14.3 PHARMACOKINETIC PARAMETERS AND ANALYSIS

Pharmacokinetic parameters (AUCt, AUCinf, Cmax, tmax, t½, kel, Cl/F, Vd/F) will be estimated following noncompartmental analysis of plasma concentration time-course data for Clopidogrel, AT -10 (2-oxo-clopidogrel), and MP-H4. PK parameters at steady-state will be estimated for Clopidogrel, AT - 10(2-oxo-clopidogrel), and MP-H4. Statistical comparison of the single-dose and multiple-dose PK parameters of peak (Cmax) and total (AUCt, AUCinf) exposure for the AT-10 and MP-H4 will be made between the AT-10 and Clopidogrel dose groups; between and within metabolizer groups. Additionally, geometric means will be calculated for AUCt, AUCinf, and Cmax. Analyses of variance (ANOVA) will be performed on the ln-transformed PK parameters AUCt, AUCinf, and Cmax. Each ANOVA will include calculation of least-squares means (LSMs), the differences between adjusted means, and the standard error associated with these differences. Ratios of means will be calculated using the LSM for Lntransformed AUCt, AUCinf, and Cmax. Although this is not a bioequivalence study, statistical comparison of the PK of AT-10 and MP-H4 between the AT-10 and Clopidogrel dose groups will be performed.

CONFIDENTIAL

Page 62 of 74

Although this is not a bioequivalence study following PK comparison will be made:

- PK comparisons will be made for AT -10 and MP-H4 from AT -10 treatment in extensive metabolizers versus Clopidogrel treatment in extensive metabolizers
- PK comparisons will be made for AT -10 and MP-H4 from AT -10 treatment in poor metabolizers versus Clopidogrel treatment in poor metabolizers
- PK comparisons will be made for AT -10 and MP-H4 from AT -10 treatments in extensive metabolizers versus AT -10 treatments in poor metabolizers.

The 90% confidence interval of the relative mean (geometric least square mean) of AT -10 and MP-H4 from AT -10 treatment versus Clopidogrel treatment for Ln-transformed Pharmacokinetic parameters Cmax, AUCt, AUC(0-inf) will be computed. Other PK comparison will be made if deemed appropriate.

C _{max}	Maximum measured plasma concentration over the time span specified		
T _{max}	Time of the maximum measured plasma concentration. If the maximum		
	value occurs at more than one time point, T _{max} is defined as the first time		
	point with this value		
AUC _{0-t}	Area under the concentration-time curve from time zero to the last sample		

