14.4 PHARMACODYNAMIC EFFECT ANALYSIS

ADP induced platelet aggregation will be assessed for change from baseline in each treatment group at each time point assessed on each dosing day (0.5, 2 and 6 hours post dose) and 24 hrs post dosing of last dosing day in each period. The change over time for each parameter will also be assessed.

Platelet inhibition will be calculated as per below formula.

Platelet Inhibition = $(1 - \text{Residual Impedance} / \text{Baseline Impedance}) \times 100$

The results will be reported as either residual platelet aggregation, measured as maximal amplitude of impedance (ohms), or platelet inhibition. The data from treatment groups 1 and 3 will be combined in the CONFIDENTIAL Page 63 of 74

analysis and similarly for treatment group 2 and 4 will be combined in the analysis. Statistical comparison will be made between the change from baseline at each time point between the treatment groups 1 and 3 (extensive metabolizers) versus treatment groups 2 and 4 (poor metabolizers) for each treatment (AT -10 and Clopidogrel). If applicable, as clinical phase of study will be conducted in group of volunteers not more than 18, volunteer group effect will also be analyzed statistically.

The incidence of signs of bleeding from the abbreviated physical examination and the incidence of abnormal liver function tests (ALT, AST, total bilirubin, and alkaline phosphatase) will be tabulated for the treatment groups. The incidence of these events will not be formally tested and the comparison will be observational only. The observational comparisons will be made between the AT -10 and Clopidogrel in the extensive metabolizers and poor metabolizers.

Additionally, the relationship between the PK of MP-H4 and pharmacodynamic measurements will be addressed using population PK-PD analysis.

CONFIDENTIAL

Page 64 of 74

Ipca Laboratories Ltd Version 1.0 (Amendment 3.0)

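### The rationale compares the size of the CYP2C19 effect between the two drugs, but the plan names no genotype-by-treatment contrast with a confidence interval

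*Protocol*

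**What the plan says.** Protocol Section 6.2 gives the reason for studying both genotypes: "The response to AT-10 may not be influenced by genetic CYP2C19 polymorphisms to the extent of its influence in clopidogrel". Section 5 makes the same argument. Section 7.1 plans 20 extensive and 20 poor metabolizers, each receiving both drugs in a crossover.

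For PD, the synopsis and Section 14.4 name one statistical comparison of change from baseline at each time point. The synopsis words it as "between the Groups 1 and 3 (extensive metabolizers) versus Groups 2 and 4 (poor metabolizers) for each treatment (AT -10 and Clopidogrel", and Section 14.4 words it as "between the treatment groups 1 and 3 (extensive metabolizers) versus treatment groups 2 and 4 (poor metabolizers) for each treatment (AT -10 and Clopidogrel". No other PD test is named.

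For PK, the synopsis and Section 14.3 list three comparisons for AT-10 and MP-H4:

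- "from AT -10 treatment in extensive metabolizers versus Clopidogrel treatment in extensive metabolizers"
- the same drug comparison in poor metabolizers
- "from AT -10 treatments in extensive metabolizers versus AT -10 treatments in poor metabolizers"

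Extensive versus poor metabolizers on clopidogrel is not on the list. The 90% confidence interval in Section 14.3 is for AT-10 relative to clopidogrel. A general sentence there mentions comparisons between and within metabolizer groups, and a closing clause allows further PK comparisons at discretion. Neither names a genotype-by-treatment contrast.

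**The concern.** The hypothesis is relative and the named comparisons are not. Two genotype tests, one per drug, each ask whether that drug has a genotype effect. Neither asks whether the effects differ. If clopidogrel came out significant and AT-10 did not, a reader could take that as support for the rationale, although the same pattern can arise by chance when genotype affects both drugs equally.

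The sponsor's own data make relative size the informative quantity. Section 5 reports that omeprazole, a CYP2C19 inhibitor, reduced the effect of AT-10 on platelet inhibition by 40–50% after the loading dose and by 20–50% during maintenance. Some dependence of AT-10 on CYP2C19 is therefore plausible, and the open question is whether it is smaller than for clopidogrel.

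**Working it through.** **Plan's own figure.** There is no power calculation to reproduce. Section 8 says the size does not come from a statistical calculation. The count checks: 4 groups × 10 = 20 + 20 = 40.

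**What the planned comparisons determine.** Write AE, AP for the mean response (ln scale for PK) on AT-10 in extensive and poor metabolizers, and CE, CP for clopidogrel. The quantity in the rationale is

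Δ = (CE − CP) − (AE − AP).

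- PD: CE − CP and AE − AP are both planned, so their difference gives a point estimate of Δ. Both come from the same subjects, so the standard error also needs the between-drug covariance.
- PK: AE − CE, AP − CP and AE − AP are planned. Then Δ = (AP − CP) − (AE − CE). The unlisted clopidogrel comparison is CE − CP = (AE − AP) − (AE − CE) + (AP − CP).

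Point estimates are therefore recoverable. What is missing is a named contrast with its interval.

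**How often two separate tests mislead.** The documents give no variances, so these inputs are assumed: SD 1 for each drug, correlation ρ of 0.3 to 0.7 between a subject's two responses, the same true genotype effect on both drugs, and two-sided 5% t tests with 20 per genotype. Period and carry-over effects are ignored. Simulation used 40,000 trials per setting for effects 0.4, 0.8 and 1.0, and 20,000 for the others. Percentage of trials with clopidogrel significant and AT-10 not:

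| True effect on both drugs (SD) | 0.4 | 0.5 | 0.65 | 0.8 | 0.9 | 1.0 | 1.2 |
|---|---|---|---|---|---|---|---|
| ρ = 0.3 | 15.2 | 18.3 | 20.1 | 17.6 | 13.7 | 9.9 | 3.5 |
| ρ = 0.5 | 13.0 | 15.4 | 17.1 | 14.8 | 11.5 | 8.3 | 3.2 |
| ρ = 0.7 | 9.9 | 11.5 | 12.9 | 11.4 | 8.6 | 6.8 | 2.7 |

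The peak is near 0.65 SD, where each test has about 52% power and the two results often disagree. A two-sided 5% test of Δ errs in about 5% of trials, so about 2.5% in the direction favouring AT-10.

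**When the effects really differ.** With 0.6 SD on AT-10 and 1.4 SD on clopidogrel, the two-test pattern appears in about 54% of trials. The test of Δ has 55%, 69% and 89% power at ρ = 0.3, 0.5 and 0.7.

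**Precision of the contrast.** Each per-drug genotype difference has SE = √(2/20) = 0.316 SD. For Δ, SE = √(2(1 − ρ) × 2/20):

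- ρ = 0.3: √0.14 = 0.374
- ρ = 0.5: √0.10 = 0.316
- ρ = 0.7: √0.06 = 0.245

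Multiplying by 1.96 + 0.84 = 2.80 gives the difference detectable with 80% power: 1.05, 0.89 and 0.69 SD.

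**The case against.** The strongest reply is that the lesser influence of genotype is a hedged rationale and not an objective. Section 6.1 asks for safety, AT-10 versus clopidogrel on aggregation in each genotype, dose confirmation and PK. Section 8 calls the PD data proof of concept. This stands, and it limits the weight of the point. It does not remove it, because the two-genotype crossover is built around that rationale and the protocol lists its comparisons in two places without the matching one.

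A reader might infer that the relative effect can never be estimated, or that the PK list leaves the clopidogrel genotype effect unknowable. The algebra above shows otherwise. For PK, an approximate interval could even be assembled from the two within-genotype standard errors, since they come from different subjects. That would still be an unplanned step.

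A reader might also infer that the protocol intends to conclude that AT-10 is spared from a difference in significance. It states no such rule. The 7 to 20% is the error rate of that inference if someone draws it. It depends on the assumed effect size: about 3% at 1.2 SD, below 1% at 1.4 SD and about 2% with no effect. Comparing *1/*1 with two loss-of-function alleles could well give a large effect on clopidogrel.

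A further temptation is to add that sex confounds the genotype comparison, because Section 5 reports that "less inhibition of ADP-induced platelet aggregation was observed in women". That comes from a small study with no size given, and the protocol states no model terms from which to conclude that sex is left out. A sex effect equal on both drugs cancels from Δ. The point does not rest on it.

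Finally, model terms and covariates commonly belong in a statistical analysis plan, which is not shown. The choice of comparisons is different here, because the protocol has already stated it.

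**Conclusion.** The point holds in a limited form. The named comparisons do not match the relative claim in the rationale, and no interval or test for the difference in genotype effects is planned. Separate per-drug results cannot stand in for it: with equal effects of 0.4 to 1.0 SD, discordant significance favouring AT-10 arises in about 7 to 20% of trials, falling to about 3% at 1.2 SD. These figures rest on the assumed effect sizes, unit SDs and correlations of 0.3 to 0.7.

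It does not follow that the contrast should be the sole basis for conclusions. The AT-10 versus clopidogrel comparison within poor metabolizers uses randomised sequences and answers the stated primary objective directly.

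**What to change.** In the synopsis and Sections 14.3 and 14.4:

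1. Add the genotype-by-treatment contrast, defined as the extensive-versus-poor comparison of each subject's AT-10 minus clopidogrel difference. Apply it to platelet inhibition and to ln MP-H4 AUC and Cmax. A mixed model with sequence, period, treatment, genotype and treatment-by-genotype terms would supply it.
2. Report it as an estimate with a confidence interval whose level is fixed in advance.
3. List the clopidogrel extensive-versus-poor PK comparison explicitly.
4. State that any claim of lesser genotype influence on AT-10 rests on this contrast, read alongside the within-genotype AT-10 versus clopidogrel comparisons. For PD, name those comparisons too, since Section 14.4 does not.

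The cost is wording and a little programming, because the crossover already collects the data. The drawback is precision: with 20 per genotype, 80% power is reached only for differences of about 0.7 to 1.05 SD under the stated assumptions. A wide interval that includes zero should not be read as showing equal genotype effects.
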